There will be no active vaccination with Ad26.COV2.S of neonates/infants in this study.

Previously vaccinated participants (Groups 1-3), will receive a single dose of Ad26.COV2.S at 5×10^{10} vp as part of the study. No further vaccinations will be received by these groups during the study.

A booster vaccination with a single dose of Ad26.COV2.S at 5×10^{10} vp will be offered to vaccine naïve consenting participants who have completed pregnancy, are not pregnant again, and haven't received another COVID-19 vaccine (eg, national immunization program). The booster vaccination for vaccine naïve participants at study entry should be administered not earlier than 2 months after the participant's Ad26.COV2.S vaccination in the study. The study duration will not be extended. Dose 2, in this document refers to Booster which is only applicable for Group 4.

Safety assessments include an observation period at the study site after vaccination to monitor for the presence of any severe acute reactions, the recording of any solicited local or systemic adverse events (AEs), unsolicited AEs, serious AEs (SAEs), adverse events of special interest (AESI), pregnancy-related AEs throughout pregnancy, and medically attended adverse events (MAAEs).

Other safety assessments include clinical laboratory assessments, vital signs measurements (pulse/heart rate, supine systolic and diastolic blood pressure, respiratory rate, and body temperature) and physical examinations. In addition, adverse maternal/fetal outcomes, adverse neonate/infant outcomes SAEs (including MIS-C), MAAEs and AEs leading to discontinuation will be recorded.

Active surveillance for COVID-19-like signs and symptoms in participants and neonates/infants will occur, including a COVID-19 surveillance (symptom check) through the participant's electronic diary (electronic clinical outcome assessment [eCOA]). Participants will be asked to confirm whether subjective changes in (postpartum) breast milk production (reduction) have been noticed and report changes in the eCOA diaries. Confirmed SARS-CoV-2 infection will be recorded.

Individuals who do not meet the criteria for participation in this study (screen failure) may be rescreened on 1 occasion only. Participants who are rescreened will be assigned a new participant number, undergo the informed consent process, and then restart a new screening phase.

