follow-up 2'

max PN D183

(neonates); i.e. PN D43 to

	Phase		Period		Interval
Phase	#	Period	#	From	То
'Postnatal follow-up 3' (neonates); i.e. PN D183 to max PN D366	7			One minute after Postnatal follow-up 2 period ends	 Minimum of : g) Maximum of 23:59 at the date of last contact (for early discontinuation) and 23:59 at the date of last visit h) 23:59 at the date of data base cut-off date in case of interim analysis i) D366 after birth j) One minute before date and time of another COVID-19 vaccination outside the study k) One minute prior to end of the study visit
'Post-dose' (Booster)	2	Post-dose 2 (i.e. Post- Booster)	2	Date and time of second vaccination (i.e. Booster)	 Minimum of: a) 23:59 at the date of last contact (for early discontinuation) b) 23:59 at the date of data base cut-off date in case of interim c) 23:59 on 28 days after the Booster Vaccination (23:59 of that day + 28 days) d) One minute before date and time of another COVID-19 vaccination outside the study
Booster follow-up 1	8			One minute after post-dose 2 period ends	 Minimum of: a) 23:59 at the date of last contact (for early discontinuation) b) 23:59 at the date of data base cut-off date in case of interim c) One minute prior to 6 months after Booster Vaccination d) One minute before date and time of another COVID-19 vaccination outside the study
Booster follow-up 2	9			One minute after Booster follow-up 1	 Minimum of: a) Maximum of 23:59 at the date of last contact (for early discontinuation) and 23:59 at the date of last visit b) 23:59 at the date of data base cut-off date in case of interim c) One minute before date and time of another COVID-19 vaccination outside the study e) One minute prior to end of the study visit
Follow-up other vaccine	10			Date and time of viral vaccination outside the study	 Minimum of: a) Maximum of 23:59 at the date of last contact (for early discontinuation) and 23:59 at the date of last visit b) 23:59 at the date of data base cut-off date in case of interim analysis c) Date and time of end of the study visit

Note: PP Dx = Postpartum Day x, PN Dx = Postnatal Day x

Adverse Events (AE) tables and selected other tables may display AEs (or other counts) by phase. For such tables, post vaccination periods can be combined and additionally displayed. The "active" periods can be defined as:

- "Post-Dose 1"
- "Post-Booster", where applicable (booster)
- "Post-Dose 1 and Post-Booster Combined", where applicable.

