5.4. Secondary Endpoints Analysis

5.4.1. Definition of Endpoints

Safety and reactogenicity of Ad26.COV2.S booster vaccination in adult participants

- Solicited local and systemic AEs for 7 days after (each) vaccination, or until resolution
- Unsolicited AEs for 28 days after (each) vaccination
- SAEs and AESI throughout the study (from vaccination until end of the study, i.e. at least 12 months after delivery)
- MAAEs until 6 months after the last vaccination

• AEs leading to study discontinuation (from vaccination until end of the study)

Refer to Sections 5.6.1 for more details on adverse events definitions.

Pregnancy Outcomes

Pregnancy outcomes in adult participants (including live term birth, live preterm birth, stillbirth, and abortion). Data are captured in the Delivery History eCRF.

Pregnancy-related AEs

Pregnancy related AEs in adult participants, including gestational diabetes, gestational hypertension, premature rupture of membranes, premature labor, premature uterine contractions, poor or restricted fetal growth, pre-eclampsia, eclampsia, vaginal or intrauterine hemorrhage (non-exhaustive).

The complete list of preferred terms to be included as pregnancy related AEs is provided in Section 6.8. Refer to Sections 5.6.1 for more details on adverse events definitions.

Safety in neonates/infants

- SAEs (including Multisystem Inflammatory Syndrome in Children [MIS-C]) and AESIs in neonates/infants from birth to approximately 12 months of age.
- MAAEs for neonates/infants from birth until 6 months of age.
- AEs in neonates/infants leading to study discontinuation from birth until discontinuation.

Refer to Sections 5.6.1 for more details on adverse events definitions and Section 6.9 for MIS-C.

Neonate/infant Outcomes

Neonate/infant outcomes (including normal neonate, term neonate with (or without) complications, preterm neonate with (or without) complications, neonatal infection, respiratory distress, congenital anomalies, neonatal death, low birth weight, and small for gestational age measured from birth until approximately 12 months of age) (non-exhaustive). Data are captured in the Neonatal Medical History eCRF.

Humoral Immune Response in peripheral blood of adult participants

- Serological response to vaccination as measured by ELISA (S-ELISA; EU/mL]) at all blood collection timepoints.
- Serological response to vaccination as measured by VNA titers, 28 days after the first vaccination.

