5.6.1.3. Analysis of Adverse Events

Solicited AEs (shown in output) are extracted from the investigator assessment pages of the CRF and will be recorded in the Clinical Event SDTM domain. Only Solicited AEs with onset within 7 days after vaccination (post-dose 1, post-booster [booster in Group 4], and post-dose 1+ post-booster) will be reported in tables. For unsolicited AEs, only the AEs within the 28-day period following (primary or booster) vaccination will be presented in the safety tables except for SAEs, AEs leading to treatment/study discontinuation (incl. MAAE leading to treatment/study discontinuation) and AESIs which will be captured and tabulated in the outputs covering the whole study period (i.e. up to 12 months postpartum), and MAAEs which will be captured and tabulated for all participants from the first vaccination until 6 months after (each) vaccination.

Number and percentage of participants with at least one particular AE (unsolicited/solicited) will be tabulated. Unsolicited AEs will be summarized by System Organ Class and Preferred Term. Solicited AEs will be summarized by class (administration site/systemic) and Preferred Term.

For solicited AEs following tables will be provided: summary, by worst severity grade, at least grade 3, related (systemic only), time to onset (in days) and duration (in days) for most frequent events (>5%) and body temperature. Note: Duration is defined as number of days from the start of the event until resolution of the event. The time to first onset is defined as (date of first onset – reference date + 1). The reference date is the start date of the vaccination period.

For unsolicited AEs, the following tables will be provided: summary table (including SAE, AESI, MAAEs, AEs leading to treatment/study discontinuation, fatal outcome, and discontinuation), all events, most frequent (>5%), at least grade 3, related, and SAEs. The proportion of AEs resulting in a medically attended visit (other than routine health maintenance visits) will also be tabulated.

Pregnancy-related AEs in adult participants (including gestational diabetes, gestational hypertension, premature rupture of membranes, premature labor, premature uterine contractions, poor or restricted fetal growth, pre-eclampsia, eclampsia, vaginal or intrauterine hemorrhage [non-exhaustive]) will be tabulated separately. The complete list of preferred terms to be included as pregnancy related AEs is provided in Section 6.8.

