5.6.1.5. Missing Data

Missing data will not be imputed. Participants who do not report an event will be considered as participants without an event. An AE with a missing severity or relationship will be considered as an AE reported, but will be considered as not reported for the severity or relationship. For example, an AE with missing severity will be considered as an AE reported for the analysis of any grade but will be considered as not reported for the analysis of at least grade 3.

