6.5. Appendix 5 Prior and Concomitant Medications

Prior and Concomitant medications will be coded using the World Health Organization Drug Dictionary (WHO-DD).

Prior medications are defined as any therapy used before the day of first dose (partial or complete) of study intervention. Concomitant medications are defined as any therapy used on or after the same day as the first dose of study intervention, including those that started before and continue on after the first dose of study intervention.

For all participants, concomitant therapies associated with an SAE, a suspected AESI, MAAEs, AEs leading to discontinuation will be recorded in the eCRF. The proportion of participants with concomitant medication associated with these events will be tabulated.

For all participants, concomitant therapies associated with COVID-19 infection will be captured in the electronic eCRF for the duration of the study. Duration of the study is from the first dose date till end of study (date of last visit PP366) or trial discontinuation, whichever occurs first. The proportion of participants with new concomitant medication associated with these cases will be tabulated. New concomitant medications are defined as medications not available at baseline or medication with an increased dosage (See below, New Concomitant Medications, for details), compared to baseline. Baseline medications are all medications reported prior to and at the day of first vaccination. In case a baseline medication is reported multiple times then only the last available record reported prior to or at the day of first vaccination will be used.

Concomitant therapies associated with unsolicited AEs will be collected, recorded in the eCRF from the time of first and second vaccination through 28 days after post-dose 1 or post-booster and the proportion of participants with concomitant medication will be tabulated. Concomitant therapies associated with solicited AEs will be collected by the participants, recorded in the eCRF from the time of first or second vaccination through 7 days after post-dose 1 or post-booster and the proportion of participants with concomitant medication will be tabulated.

Based on their start and stop date, concomitant therapies will be reported in each applicable phase.

If a concomitant therapy record is missing components of its start and/or stop dates (time, day and/or month and/or year):

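### A Group 4 woman boosted after about postpartum Day 183 cannot complete the 6-month booster MAAE window, yet counts in full as event-free, and Table 3 lets her booster phases run past her last visit

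*SAP*

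**What the plan says.** Section 1.2 offers the booster to consenting vaccine-naïve women who "have completed pregnancy, are not pregnant again" and have had no other COVID-19 vaccine. It "should be administered not earlier than 2 months after the" first study dose. The SAP gives this earliest date but no latest one, and adds that "The study duration will not be extended". Appendix 5 (6.5) describes the study as running "till end of study (date of last visit PP366".

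The secondary booster safety endpoints in 5.4.1 include "MAAEs until 6 months after the last vaccination". Section 5.6.1.3 has MAAEs "tabulated for all participants from the first vaccination until 6 months after (each) vaccination". Percentages are head counts within population and phase (5.1). Section 5.6.1.5 adds: "Participants who do not report an event will be considered as participants without an event".

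In Table 3 (5.1.2), Booster follow-up 1 ends at the earliest of last contact (for early discontinuation), an interim data cut-off, another COVID-19 vaccine, or "One minute prior to 6 months after Booster Vaccination". Post-dose 2 has the same list with 28 days in place of 6 months. Booster follow-up 2 alone also lists the last visit and the end-of-study visit. Section 5.7.6 summarises the interval from first dose to booster, but not the follow-up after it.

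**The concern.** The start of the booster window can move while the end of the study is fixed, so follow-up shortens as the booster gets later. The planned percentage ignores this. A woman boosted with 60 days left counts the same as one followed for the full 6 months, and her silence is read as no event. Any error from this source makes the booster look safer.

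Separately, no ending rule in Table 3 fits a woman who completes the study before 28 days or 6 months have passed since her booster. She did not discontinue early, there is no interim cut-off, and she had no other vaccine. Her phase end then falls on a date after she has left the study.

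**Working it through.** **Inputs.** The last adult visit is postpartum Day 366 (SAP 6.5). The MAAE window is 6 months, taken as 183 days. Booster day X is not given in the SAP, so every distribution of X below is an assumption. So is the true 6-month risk R. The SAP states no figure for booster follow-up, so there is none to reproduce.

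**Step 1: cut-points.** The window is complete if 366 − X ≥ 183, that is X ≤ 183. The 28-day unsolicited window is truncated only for boosters in about the last 28 days, since 366 − 28 = 338.

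**Step 2: share of the window observed**, min(1, (366 − X)/183):

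| Booster day | Days left | Share observed |
|---|---|---|
| 183 or earlier | 183 or more | 100% |
| 214 | 152 | 83% |
| 245 | 121 | 66% |
| 275 | 91 | 50% |
| 306 | 60 | 33% |
| 337 | 29 | 16% |

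**Step 3: average over assumed uniform timings.** For X uniform on [a, b], the share incomplete is (b − 183)/(b − a). Mean observed days are [183(183 − a) + (183² − (366 − b)²)/2]/(b − a).

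- Days 46–338: 155/292 = 53% incomplete. (25,071 + 16,352.5)/292 = 141.9 days, or 78% of 183.
- Days 43–270: 87/227 = 38% incomplete. (25,620 + 12,136.5)/227 = 166.3 days, or 91%.
- Days 46–366: 183/320 = 57% incomplete. (25,071 + 16,744.5)/320 = 130.7 days, or 71%. About 9% (28/320) have under 28 days.

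**Step 4: effect on the percentage.** Assume a constant hazard, R = 20%, and booster timing unrelated to risk. A woman observed for share f has observed risk 1 − 0.8^f. Averaging this over X gives the expected crude percentage:

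| Assumed timing | Crude, as planned | Relative shortfall |
|---|---|---|
| Days 46–338 | 15.7% | 21% |
| Days 43–270 | 18.3% | 8% |
| Days 46–366 | 14.5% | 28% |

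For Days 46–338, the 53.1% boosted late have average observed risk 11.9%, so 0.469 × 20% + 0.531 × 11.9% = 15.7%.

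A different form of assumption gives a similar picture. If 25% of women are boosted on Day 306 and the rest by Day 183, late risk is 1 − 0.8^(60/183) = 7.1%. The crude figure is 0.75 × 20% + 0.25 × 7.1% = 16.8%, a 16% relative shortfall. Over R of 10–40%, a late share of 10–50% and late booster days 245–306, the shortfall runs from about 3% to 33%.

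**Step 5: Table 3 dates, with no timing distribution needed.** Take a completer boosted on Day 300. Booster follow-up 1 ends near Day 300 + 183 = 483. Booster follow-up 2 starts one minute later but must end by about Day 366, so its end precedes its start. Table 4 takes the maximum of the phase ends, so the overrun passes into the Booster Vaccination Period and Entire Study. Section 5.6.1.4 imputes a completely missing adverse event end date for completers from the end of the last period, which can then fall after the last visit.

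**The case against.** The strongest objection is that the protocol, which is not at hand, may set a latest booster date. If that date is no later than about Day 183, no MAAE window is truncated. Many women could also have been boosted early: enrolment was at Weeks 16 to 38, and a woman dosed well before term is already 2 months past that dose at delivery. A reader might infer that the booster MAAE percentage is certainly biased, or biased by a known amount. The SAP does not support that. It leaves the bias open, and the sizes above are scenarios.

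A reader might also infer that the missing limit in Table 3 causes the low percentage. It does not. No events are collected after the last visit and the denominator is a head count, so correcting the phase ends adds no event. Its only effect on a denominator is that women boosted in the last 28 days would leave the Booster follow-up 1 count, and they would still be in the Booster Vaccination Period. The date fault and the denominator fault need separate repairs.

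Nor does the SAP promise a 6-month cumulative risk. It sets 6 months as the limit for tabulating MAAEs, and crude incidence is an ordinary convention. That is fair, but a reader of a table built on that limit has no planned output showing how much of the window was observed.

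Finally, the analysis is descriptive, the booster optional, and the Group 4 target only at least 25. In 25 boosted women, moving from 20% to 16.8% is 0.8 of a woman, and the exact 95% interval for 5/25 is 6.8% to 40.7%. This limits the consequence, though the percentages are the whole booster safety result.

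**Conclusion.** The point holds in two parts. First, Table 3 gives impossible or overrunning phase dates for any completer boosted too late to finish Post-dose 2 or Booster follow-up 1. This follows from the text and needs only one such woman. Second, the crude booster MAAE percentage is biased downward if, and only if, boosters were given after about postpartum Day 183. The size is unknown: about 8% to 28% relative at R = 20% under the three uniform timings, assuming a constant hazard and timing unrelated to risk. It is smaller if boosters cluster early, and zero if all were given by about Day 183. The 28-day unsolicited table is touched only by boosters in the last four weeks or so. Correction is worthwhile because it is cheap and the planned outputs would not reveal the problem.

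**What to change.** 1. In Table 3, add the date of last visit or end-of-study visit to the minimum that ends Post-dose 2 and Booster follow-up 1.
2. In 5.4.1 and 5.6.1.3, define booster MAAEs as running until 6 months after booster or end of study, whichever is first.
3. In 5.7.6, add the duration of post-booster follow-up and the number of women with a complete 6-month window.
4. Beside the crude percentage, report one of two figures. One is the first-event rate per person-time in all boosted women. The other is a percentage restricted, in numerator and denominator alike, to women whose booster was at least 6 months before their scheduled study end, whether or not they had an event.

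The denominator in item 4 must depend on booster date only. A tempting variant keeps women with a complete window plus any late-boosted woman who had an event. That selects on the outcome. Under Step 4's assumptions it gives 0.157/(0.469 + 0.531 × 0.119) = 29.5% for Days 46–338, and 27.1% and 29.7% for the other two timings, against a true 20%. It is further from the truth than the planned figure and should not be used.

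The cost is SAP wording, one extra column, and a complete-window denominator that may be small. No change to booster timing is proposed. The sponsor should reconcile the booster-timing passage in 1.2 with the 6-month follow-up in 5.4.1 and 5.6.1.3.

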2. STATISTICAL HYPOTHESES

No formal statistical hypothesis is to be tested. The study is designed to provide descriptive information regarding the safety, pregnancy outcomes, and immunogenicity of Ad26.COV2.S in adult participants in the 2nd and/or 3rd trimester of pregnancy, as well as the safety and outcomes of neonates/infants. In addition, the study will provide descriptive information regarding the safety and immunogenicity of Ad26.COV2.S administered as a booster in eligible participants.

3. SAMPLE SIZE DETERMINATION

The number of adult participants that will be assessed for safety and reactogenicity of the Ad26.COV2.S vaccine, from Week 16 of pregnancy through to delivery/termination and up to 12 months postpartum, was chosen to provide a preliminary assessment of safety and immunogenicity in this population.

A target of 240 adult participants in the 2nd or 3rd trimester of pregnancy, ≥ 18 to ≤ 45 years of age was planned to be enrolled in this study. The sample size of each of the groups (Groups 1 to 4) was preferably equally distributed but was flexible with a target to recruit at least 40 participants in Groups 1 to 3 and at least 25 participants in Group 4. Participants were stratified by pregnancy stage at the time of enrollment (refer to Section 5.7.5 for details), with a goal of at least approximately 25% participants per trimester, per group.

As of CTP amendment 7, participant enrollment in this study ceased.

When 40, 60, 120 and 240 participants are vaccinated, the observation of 0 AEs would be associated with a 95% confidence (2-sided) that the true rate is less than 8.8%, 6%, 3% and 1.5% respectively (additional cases are provided in Table 1).

True Adverse	Probability of observing at least one adverse event given a true adverse event rate					
Event Rate	N=40	N=60	N=120	N=240		
0.5%	18%	26%	45%	70%		
1.0%	33%	45%	70%	91%		
1.5%	45%	60%	84%	97%		
2.0%	55%	70%	91%	99%		
2.5%	64%	78%	95%	>99%		
3.0%	70%	84%	97%	>99%		
5.0%	87%	95%	>99%	>99%		
N: number of par	ticipants receiving stu	dy vaccine (Ad26.COV2	.S).			

Table 1:	Probability of Observing at Least One Adverse Event
----------	---

5. STATISTICAL ANALYSES

5.1. General Considerations

A baseline (or reference) value will be defined as the value of the last available assessment prior to the first vaccination on Day 1, where Day 1 is the date of first vaccination for adults. A value at birth is baseline value for neonates and the birth date is the neonate reference date. The neonate baseline values for immunogenicity analysis are those from the cord blood sample collected.

Every adult will have a unique subject ID in the ADaM datasets and every neonate will have the same unique subject ID with 'A' added at the end of the ID. Multiple pregnancies [twins or higher order multiples] are excluded from the study but if a participant with multiple pregnancy is inadvertently enrolled, neonates will have the same unique subject ID with 'A', 'B', 'C' and D added at the end of the ID based on the number of neonates.

Unless otherwise specified, continuous variables will be summarized using the following statistics, as appropriate: number of observations, arithmetic mean (mean), standard deviation (SD), standard error (SE), median, minimum, and maximum. Frequencies and percentages (one decimal place) will be generated for categorical variables. Denominator for the percentages is the number of participants in the considered population, and phase (where applicable; incidence per 100 participants/phase).

No formal statistical testing is planned. The safety analysis will be performed on the FAS-A based on actual intervention received and the FAS-NVN, unless otherwise specified. Safety data will be presented by period/phase (as applicable) as well as over the entire study. Immunogenicity results will be conducted on the PPI-A and PPI-NVN and presented per scheduled time point as appropriate. Safety and immunogenicity endpoints will be summarized descriptively by previous vaccination group (as defined in Section 1.2) and overall. All listings will include the previous vaccination group. Vaccination schedule in Group 4 (i.e. vaccine-naive at study entry) will have two components: the Primary Vaccination and the (optional) Booster Vaccination. Listings will be shown per phase and time point, as appropriate.

Participants that took another COVID-19 vaccine during the study are excluded from all safety and immunogenicity analyses from the moment they received the other vaccine. The safety data from those participants after they received the other vaccine will be listed separately.

Other exploratory or sensitivity analyses, on an ad-hoc basis, may be performed in addition to the analyses described in this document.

For adults, study Day 1 or Day 1 refers to the start of the first study vaccination. For neonates, study Day 1 or Day 1 refers to the neonate birth. Unless specified otherwise, safety assessments at all visits will be assigned a day relative to those dates (respectively for adults and neonates). In addition, in Group 4, safety assessments occurring after the booster vaccination date will also be assigned a day relative to this date.

Study day and relative day are defined as follows:

For adults (Day 1 refers to the start of the first study vaccination):

- Study Day=visit date-date of Day1+1; if visit date ≥ date of Day 1
- Study Day=visit date-date of Day1; if visit date < date of Day 1

For neonates (Day 1 refers to the neonate birth):

- Study Day=visit date-neonate birth date+1; if visit date \geq date of Day 1
- Study Day=visit date-neonate birth date+1; if visit date < date of Day 1

Relative day (relday), the number of days in the analysis time point will be defined as:

- relday = visit date reference date+1 for visits on or after the reference date,
- *relday = visit date reference date* for visits before the reference date,

where the reference date equals the date of the first study vaccination for adults, and as well as the date of booster vaccination for participants in Group 4, and the neonate birth date for the neonates.

For laboratory and vital signs all time points (including unscheduled ones, if any) are also considered in the determination of the worst toxicity grade.

Unscheduled results or multiple results for laboratory and vital signs taken at the same visit will be reported in listings.

